5. STUDY DESIGN

[figure not shown]
5.1. Overall Design

Protocol waivers or exemptions are not allowed with the exception of immediate safety concerns that may arise after the oral administration of CAB. Therefore, adherence to the study design requirements, including those specified in the SoA Table (Table 1), is essential and required for study conduct.

This study is an open label (OL) Phase 1, multi-site, study to evaluate the PK, safety, tolerability, and acceptability of CAB LA in adult male participants (Figure 1). Eligible participants will receive OL CAB LA. Participants will receive daily oral CAB (30 mg tablets) for 4 weeks during the Oral Phase of the study, to assess for safety and tolerability prior to receiving CAB LA injections. Serial PK will also be performed during the oral phase to characterize plasma PK parameters of distribution and elimination. Following safety assessments after 4 weeks of oral dosing, participants will enter the Injection Phase at Week 5 and receive IM injections of CAB LA (Figure 1). CAB LA 600mg will be administered as a single 3-mL IM injection. Subjects who volunteer to participate in the intensive PK assessment will have serial blood sampling for measurement of plasma CAB concentrations following oral administration over a 24 h window starting on Day 27 and ending on Day 28 (Table 2). Pharmacokinetic sampling following CAB LA IM injections will start on just prior to the first injection at Week 5 (Injection Phase) and prior to each subsequent injection with limited PK sampling between injection visits (for complete PK sampling schedule refer to SoA , Table 1).

Starting at 8 weeks post last injection, participants will be seen once every 12 weeks for 48 weeks during the follow-up phase.

Figure 1 Study Design

5.2. Number of Participants

Approximately 60 participants will be screened in order to ensure that approximately 48 participants will enter the oral phase and approximately 40 participants will enter the injection phase of the study. The participants will be enrolled from multiple sites in China. Participation will be limited to participants who are male at birth, with a target of at least 60% men who have sex with men. For further details, refer to Section 10.

If participants prematurely discontinue the oral phase of the study, additional replacement participants may be recruited at the discretion of the Sponsor. Participants who enter the injection phase of the study will not be replaced.

5.3. Participant and Study Completion

A participant is considered to have completed the study if he/she has completed all phases of the study including week 89.

The end of the study is defined as the participant completing the week 89 visit.

5.4. Scientific Rationale for Study Design

The currently proposed study will evaluate a CAB LA 600 mg IM Q8W dosing regimen is appropriate, in a Chinese population.

5.5. Dose Justification

Oral CAB 30 mg once daily has been selected as the oral lead-in dose prior to initiating CAB LA IM injections. Following this dose in HIV infected participants, geometric mean C_{τ} and C_{max} were 4.2 $\mu\text{g/mL}$ and 7.5 $\mu\text{g/mL}$, respectively. Oral CAB 60 mg once daily was safe and well tolerated in Phase 2 treatment studies and achieves geometric mean C_{τ} and C_{max} of 7.9 $\mu\text{g/mL}$ and 12 $\mu\text{g/mL}$, offering coverage for increased exposures in Chinese males due to any potential decrease in UGT1A1 metabolism. The oral lead-in period will be conducted from Day 1 through Week 4 of the study. Since participants are of low risk of HIV acquisition, oral dosing will be discontinued during safety assessments after the oral lead-in and prior to the first injection at Week 5.

The CAB LA dose rationale is based on the objective of delivering adequate drug concentrations to prevent sexual transmission of HIV. The proposed dose schedule for evaluation in humans is based on maintaining plasma CAB concentrations above the PA-90% of the maximum inhibitory concentration (IC90) value of 0.166 $\mu\text{g/mL}$ which demonstrated a 97% protective efficacy of Simian/Human Immunodeficiency Virus (SHIV) transmission in male macaques. Plasma CAB concentrations $>4 \times \text{PA-IC}_{90}$ (0.664 $\mu\text{g/mL}$) demonstrated 100% protection against intra-rectal SHIV transmission [Andrews, 2014] and was predicted to provide 90% probability of in vivo protection after seven intra-vaginal SIVmac251 challenges in female rhesus macaques [Spreen, 2015].

CAB LA has been administered following single and repeat IM injections to non-HIV infected adult males and females (n=186) and following repeat IM injections to HIV

infected participants (n=230). Relevant PK parameters observed following repeat administration of CAB LA to adults are presented in [Table 3](#).

[figure not shown]
Table 3 Summary of CAB PK Parameters following Repeat Dose Administration of CAB LA to Healthy and HIV-infected Subjects

Population	Study	CAB LA Regimen	Dosing Interval	Plasma CAB PK Parameter (Geometric mean [95%CI] (CVb%))				
				AUC(0- τ) ($\mu\text{g}\cdot\text{h}/\text{mL}$)	C _{max} ($\mu\text{g}/\text{mL}$)	C _{τ} ($\mu\text{g}/\text{mL}$)	T _{max} ^a (day post last dose)	
Healthy Subjects	LAI115428	800 mg IM/ 400 mg IM Q4W (n=10)	D1-W4	1252 [836, 1873] (61)	2.74 [1.72, 4.35] (72)	1.78 [1.35, 2.36] (41)	6 (6 – 28)	
			W4-W8	2010 [1619, 2494] (31)	3.79 [2.89, 4.99] (40)	2.60 [2.20, 3.07] (24)	6 (2 – 28)	
			W8-W12	2182 [1798, 2647] (28)	4.03 [3.05, 5.30] (40)	2.69 [2.21, 3.27] (28)	6 (2 – 28)	
			W12-W16	2473 [2063, 2965] (26)	4.41 [3.55, 5.48] (31)	3.27 [2.71, 3.94] (27)	6 (2 – 13)	
		800 mg IM Q12W x2 (n=10)	D1-W12	2917 [2045, 4161] (53)	2.70 [1.49, 4.88] (99)	0.74 [0.41, 1.32] (97)	16.5 (2 – 83)	
			W12-W24 (n=9)	4468 [3058, 6528] (52)	3.31 [2.18, 5.04] (59)	1.10 [0.50, 2.46] (140)	15 (6 – 42)	
		201120 ECLAIR	800 mg IM Q12W x3 (n=93)	D1-W12 (n=93)	3415 [3140, 3714] (42.5)	4.26 [3.64, 4.98] (88.6)	0.302 ^b [0.237, 0.385] (157)	7.76 (4.95 – 57.0)
				W12-W24 (n=89)	3873 [3543, 4235] (44.3)	5.22 [4.52, 6.04] (78.0)	0.331 ^c [0.253, 0.435] (165)	6.97 (3.83 – 75.0)
	W24-W36 (n=85)			4021 [3728, 4337] (36.2)	4.91 [4.31, 5.60] (66.6)	0.387 ^d [0.296, 0.505] (150)	6.99 (5.63 – 43.0)	
	HIV Infected Subjects	200056 LATTE2	800 mg IM/ 400 mg IM Q4W (n=115)	W24-W28 (n=97)	1858 ^e [1719, 2007] (37)	3.50 [3.2, 3.8] (39)	2.35 ^f [2.2, 2.5] (32)	6.9 (0 – 29)
W40-W44 (n=95)				2017 ^g [1847, 2203] (41)	3.50 ^j [3.3, 3.8] (37)	2.56 ^h [2.4, 2.7] (32)	6.9 (0 – 28)	
800 mg IM/ 600 mg IM Q8W (n=115)			W24-W32 (n=98)	3037 ⁱ [2786, 3310] (42)	3.55 [3.2, 3.9] (56)	1.43 ^j [1.3, 1.6] (54)	6.9 (0 – 59)	
			W40-W48 (n=104)	3027 ^k [2762, 3322] (47)	3.33 [3.1, 3.6] (47)	1.49 [1.4, 1.6] (42)	7.0 (0 – 57)	

- a. median (range)
- b. n=84
- c. n=71
- d. n=66
- e. n=84
- f. n=108
-
- g. n=80
- h. n=98
- i. n=86
- j. n=100
- k. n=112

PK data from the ECLAIR (201120) study showed only 30 to 37% of reportable CAB plasma trough concentrations were $\geq 4x$ PA-IC90 following each of the three injections, and 15 to 31% were below $1x$ PA-IC90 [Markowitz, 2016]. Graphical evaluation of the CAB concentration-time profiles suggests that absorption was more rapid among participants in the ECLAIR study than predicted, resulting in higher peak and lower trough concentrations. In the LATTE-2 (200056) study, CAB LA was evaluated in combination with Rilpivirine (RPV) LA at two dosing frequencies Q4W and Q8W. The Q8W regimen included an 800 mg loading dose and two subsequent monthly doses of CAB LA 600mg prior to initiating an every 8-week dosing interval starting at Week 8. On average, this Q8W regimen achieved clinical targets in both males and females (Figure 2), supporting the selection of an every 8-week regimen for PrEP.

[figure not shown]
Figure 2 Observed Mean (SD) Concentration-Time Data following CAB LA Q8W in HIV infected subjects (200056 (LATTE-2))

A population PK analysis has been performed to select doses for study in Phase 3 trials in treatment and PrEP using NONMEM 7.2 (ICON Development Solutions, Ellicott City, Maryland, USA) with data from eight Phase 1 and 2a studies plus the two Phase 2b studies 201120 (ÉCLAIR) and 200056 (LATTE-2). A total of 416 participants provided data following CAB LA IM administration, with approximately 50% of data obtained from LATTE-2, ~20% from ECLAIR and ~30% from Phase 1/2a studies. A two-compartment model with first order absorption characterized the observed data well. High BMI ($>30 \text{ kg/m}^2$) and female sex were associated with slower absorption rates. BMI and formulation change helped explain a minor amount of the variability of KA LA. Scaling of central volume and systemic clearance by weight also improved model fit. Model performance was assessed using various goodness-of-fit criteria, including a visual inspection of diagnostic scatter plots, successful minimization, completion of covariance step, and precision of the parameter estimates. A visual predictive check was used to validate the model.

The model was used to simulate the median (90% prediction interval (PI)) CAB concentration-time profile for the selected CAB LA PrEP regimen of 600mg IM Day 1, Week 4, then Q8W. The simulated profile for this regimen for male participants is shown in [Figure 3](#). At steady state, 50% are predicted to achieve trough concentrations above the geometric mean trough following the 10 mg oral dose of $1.35 \mu\text{g/mL}$ (8-fold PA-IC₉₀), which was shown to be efficacious in maintaining viral suppression when coadministered with in RPV 25mg once daily in LATTE, and 95% are predicted to achieve trough concentrations above PA-IC₉₀. A one week delay in dosing of 600mg IM at steady state resulted in a drop in the median C_{τ} to $1.08 \mu\text{g/mL}$ with 92% of C_{τ} values remaining above the PA-IC₉₀, supporting a maximum one week delay in dosing. Phase 3 PrEP trials with the selected CAB LA dose have started in late 2016.

Figure 3 Simulated* Median (90% Prediction Interval [PI]) Plasma CAB Concentrations versus Time for the Selected CAB LA Q8W Regimen (600 mg IM Day 1, Week 4, then Q8W) in Male Subjects with normal UGT function

Above simulation includes oral lead-in dosing up to and including the day of the first injection. In this study, however, there will be an approximately 1-week washout between the last oral dose and the first injection at Week 5.

Although race is not a significant covariate, Asian participants comprise only ~2.5% of the IM data in the current population pharmacokinetic (PK) model. Variability in the CAB LA profile is driven by absorption rate constant (which is impacted by gender and BMI) and systemic clearance, which can be affected by metabolic pathways and body size measures (weight). Adult Asian males are assumed to be similar in size to those in the model. Differences in UGT metabolism may, however, play a role in disposition of CAB LA in Asian participants.

Metabolism of CAB primarily involves UGT1A1, with a minor contribution from UGT1A9. Carriage of the UGT1A1 *28 (common) and *37 (African ancestry), and *6 (East Asian populations) alleles results in decreased UGT1A1 enzyme activity compared to wild type enzyme activity (UGT1A1 *1/*1 [Barbarino, 2014]). The clinical impact of reduced UGT1A1 enzyme activity varies between medicines. Reduced UGT1A1 enzyme

activity is associated with significant changes in disposition of irinotecan and its metabolites and, consequently, increased risk of treatment-induced toxicities [Stingl, 2014; Fujita, 2010]. In contrast, carriage of UGT1A1 polymorphisms that reduce enzyme activity have a modest effect on the oral integrase inhibitor (INI) dolutegravir exposure and its safety [Chen, 2014].

The UGT1A1*28 polymorphism has been reported to be associated with hyperbilirunemia induced by several drugs, is known to cause reduced UGT1A1 expression and predisposes individuals to Gilbert's syndrome, a benign form of episodic jaundice [Bosma, 1995; Raijmakers, 2000; Danoff, 2004; VOTRIENT Package Insert 2015, TASIGNA Package Insert, 2015]. Mild (grade 1 to 2), nonprogressive bilirubin (TBL) increases observed in a small subset of patients in LATTE might be a consequence of cabotegravir acting as a substrate of UGT1A1 [Margolis, 2015].

A pharmacogenetic (PGx) study was undertaken to evaluate the effect of *UGT1A1* and *UGT1A9* genotypes on exposure and tolerability in participants receiving oral CAB in six studies. The PGx analysis specifically examined 1) PK measurements from participants in Phase 1 and 2 studies treated with oral CAB 30 mg once daily for at least 8 days; and 2) selected tolerability endpoints using participants treated with oral CAB from a Phase 2 study.

Genetically predicted UGT1A1 activity was significantly associated with steady-state oral CAB 30mg PK parameters C_{τ} , AUC_{τ} , and C_{max} , with mean values of C_{τ} , AUC_{τ} , and C_{max} ~1.5, 1.4 and 1.3-fold, respectively, higher in participants with low relative versus normal predicted activity. Based on the cumulative CAB PK and safety data collected to date, this magnitude of increase in CAB exposure is not anticipated to have a clinically relevant impact and does not change the understood benefit-risk profile of 30mg oral CAB.

[figure not shown]
Genetically predicted UGT1A1 activity was significantly associated with change from baseline TBL, but not ALT. None of the five participants who had maximum on-treatment $TBL \geq 1.5 \times ULN$ in this dataset, had genetically predicted normal UGT1A1 activity; all carried one or more reduced function UGT1A1 alleles.

The UGT1A9 genetic variant (*1B) was not associated with any PK endpoints analyzed or with maximum on-treatment ALT, but was moderately associated with maximum on-treatment TBL. After accounting for genetically predicted UGT1A1 activity within the same model, UGT1A9 *1B is no longer significantly associated with change from baseline TBL, which suggests that the association between UGT1A9 and TBL may be due to the correlation between UGT1A1 and UGT1A9. Further details of the Pgx analysis are provided in Section 27.4 of the China Investigational New Drug (IND).

Based on the pharmacogenetics analysis, a 1.4-fold increase in AUC (0- τ) would correspond to a ~30% reduction in CL. Therefore, participants carrying a *6 allele (~10-15% in Han Chinese population) are predicted to have higher CAB concentrations following CAB LA than those (of same size and gender) with wild type UGT1A1. Simulated median (90% PI) of the proposed PrEP regimen in male participants with reduced UGT function (30% decreased CL) is shown in Figure 4. Median predicted

steady state C_{τ} has increased from 1.35 $\mu\text{g/mL}$ to 1.8 $\mu\text{g/mL}$. The median predicted steady state C_{max} (1-week post injection concentration) increased from 4 $\mu\text{g/mL}$ to 5.5 $\mu\text{g/mL}$, and the 95th percentile from 8.7 $\mu\text{g/mL}$ to 11.8 $\mu\text{g/mL}$, within the range studied following oral CAB in HIV infected participants (LATTE). Given the overall good tolerability and safety profile of CAB, it is unlikely that any increase in concentrations will produce AEs. However, there may be a predisposition to increased liver function tests (total bilirubin) in those carrying the genetic variants.

Figure 4 Simulated* Median (90% Prediction Interval [PI]) Plasma CAB Concentrations versus Time for the Selected CAB LA Q8W Regimen (600 mg IM Day 1, Week 4, then Q8W) in Male Subjects with Reduced UGT Function

6. STUDY POPULATION

Protocol waivers or exemptions are not allowed with the exception of immediate safety concerns that may arise after the oral administration of CAB.

Specific information regarding warnings, precautions, contraindications, adverse events, and other pertinent information on the investigational regimen or other study treatment that may impact participant eligibility is provided in the current Investigator's Brochures (IB) for CAB (GlaxoSmithKline Document Number [RH2009/00003/06](#), 2016).

Deviations from inclusion and exclusion criteria are not allowed because they can potentially jeopardize the scientific integrity of the study, regulatory acceptability or participant safety. Therefore, adherence to the criteria as specified in the protocol is essential.

6.1. Inclusion Criteria

Participants are eligible to be included in the study only if all of the following criteria apply:

AGE
1. Participant must be 18 to 65 years of age inclusive, at the time of signing the informed consent
TYPE OF PARTICIPANT AND DIAGNOSIS INCLUDING DISEASE SEVERITY
2. Participants are male at birth 3. Participants who have non-reactive POC HIV test and undetectable HIV-1 RNA at screening. 4. At risk of acquiring HIV, defined as having at least one casual male or female sex partner in the past 24 months 5. Healthy as determined by a responsible and experienced physician, based on a medical evaluation including medical history, physical examination, laboratory tests and cardiac monitoring at the time of screening;
INFORMED CONSENT
6. Capable of giving written informed consent, which includes compliance with the requirements and restrictions listed in the consent form.
OTHER
7. Agree to appropriate use of contraceptive measures during heterosexual intercourse. 
 • All participants should be counselled on safer sexual practices including the use and benefit/risk of effective barrier methods (e.g., male condom) to reduce the risk of sexually transmitted infections.
8. Willing to undergo all required study procedures

6.2. Exclusion Criteria

Participants are excluded from the study if any of the following criteria apply

CONCURRENT CONDITIONS/MEDICAL HISTORY (INCLUDES LIVER FUNCTION)

 1. Current or chronic history of liver disease, or known hepatic or biliary abnormalities (with the exception of Gilbert's syndrome or asymptomatic gallstones). 2. History of the following cardiac diseases: myocardial infarction, congestive heart failure, documented hypertrophic cardiomyopathy, sustained ventricular tachycardia. 3. Active skin disease or disorder (i.e., infection, inflammation, dermatitis, eczema, drug rash, psoriasis, urticaria). Mild cases of localized acne or folliculitis or other mild skin condition may not be exclusionary at the discretion of the Investigator of Record or Medical Monitor. 4. Participants determined by the Investigator to have a high risk of seizures, including participants with an unstable or poorly controlled seizure disorder. A participant with a prior history of seizure may be considered for enrolment if the Investigator believes the risk of seizure recurrence is low. All cases of prior seizure history should be discussed with the Medical Monitor prior to enrolment. 5. Any medical condition, including psychiatric conditions that in the judgment of the investigator would interfere with the participant's ability to complete study procedures. 6. Participant who, in the investigator's judgment, poses a significant suicide risk.
CONCOMITANT MEDICATIONS

 7. Use of antiretroviral (ARV) therapy (e.g., for Post exposure prophylaxis [PEP] or PrEP) in the past 30 days. 8. Use of high dose aspirin or any other anticoagulant or antiplatelet medication that would interfere with the ability to receive IM injections.
RELEVANT HABITS

 9. Assessed by the Investigator of Record or designee as being at "high risk" for HIV infection. This may include one or more of the following: 
 • The negative partner in an HIV serodiscordant couple where the HIV infected partner is not suppressed. • Men who exchange sex for goods or money. • Men who have engaged in any condomless anal intercourse within the past 6 months. • Men who have had greater than 5 male or female sexual partners within the past 6 months • Men who have had a sexually transmitted disease within the past 6 months. • Any other behaviour assessed by the investigator as "high risk". 10. History of drug or alcohol consumption that in the opinion of the Principal Investigator will interfere with study participation.

11. Ongoing intravenous drug use – episodic use or any use in the past 90 days is exclusionary (as assessed by the study investigator).
DIAGNOSTIC ASSESSMENTS AND OTHER CRITERIA
12. One or more reactive HIV test results at screening or enrolment, even if HIV infection is not confirmed. Negative HIV RNA must also be documented at screening.
13. Co-enrolment in any other HIV interventional research study (provided by self-report or other available documentation) or prior enrolment and receipt of the active arm (i.e., NOT a placebo) of a HIV vaccine trial (provided by available documentation).
14. Any of the following laboratory values during the screening period: 
 • Positive Hepatitis C antibody result • Positive Hepatitis B surface antigen (HBsAg) • Hemoglobin <11 g/dL • Absolute neutrophil count <750 cells/mm³ • Platelet count ≤100,000 cells/mm³ • Presence of a coagulopathy as defined by an international normalized ratio(INR)>1.5 or a partial thromboplastin time (PTT) >45sec • Calculated creatinine clearance <60 mL/minute using the Cockcroft-Gault equation • A single repeat test is allowed during the Screening period to verify a result, with the exception of HIV tests.
15. Participants with an alanine aminotransferase (ALT), alkaline phosphatase (ALP) or bilirubin ≥1.5xULN (isolated bilirubin >1.5xULN is acceptable if bilirubin is fractionated and direct bilirubin <35%).
16. The participant has a tattoo or other dermatological condition overlying the gluteus region which may interfere with interpretation of injection site reactions .

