8.2. Withdrawal from the Study

8.2.1. Withdrawal from the Study Treatment

A participant may withdraw from the study treatment at any time at his/her own request, or may be withdrawn at any time at the discretion of the Investigator for safety, behavioral or administrative reasons. Participants that are discontinued from treatment during the Oral Phase will end their participation at that time. Participants that are discontinued from treatment during the Injection phase will enter the post treatment period unless consent is withdrawn. All participants who have received at least 1 injection of CAB LA will be followed as per the follow-up phase of the study. Starting eight weeks post last injection, participants will be seen once every 12 weeks for up to 48 weeks. Every effort should be made to complete the early termination study procedures and observations if the participant does not enter post-treatment follow-up.

Any laboratory parameter that meets the stopping criteria should be repeated once to confirm the value prior to withdrawal

Reasons for study treatment discontinuation during the Oral or Injection Phase may include:

- Confirmed HIV acquisition
- Any clinically significant AE deemed to require discontinuation of investigational product
- Grade 3 or higher rash or Grade 2 rash with evidence of systemic involvement
- Grade 2 or higher allergic reaction
- Post entry co-enrolment in an HIV prevention study
- Use of PrEP during the course of the study
- Behaviors assessed by the investigator as being at “high risk” for HIV infection during the course of the study

These thresholds assume that participants are asymptomatic with respect to these changes. In the presence of clinically significant symptoms, lower thresholds for these parameters may need to be used for consideration of possible withdrawal of participants from the study treatment, after consultation between the Principal Investigator and a Medical Monitor.

Before discontinuing a participant from investigational product(s), the Investigator must contact the Medical Monitor. In the event that the investigator is unable to reach the

Medical Monitor, the Investigator, at his or her discretion, may withhold investigational product(s) from a participant until the Medical Monitor or designee can be contacted.

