9. STUDY ASSESSMENTS AND PROCEDURES

- Study procedures and their timing are summarized in the SoA (Section 2)
- Protocol waivers or exemptions are not allowed
- Immediate safety concerns should be discussed with the sponsor immediately upon occurrence or awareness to determine if the participant should continue or discontinue study treatment.
- Adherence to the study design requirements, including those specified in the SoA, is essential and required for study conduct.

- All screening evaluations must be completed and reviewed to confirm that potential participants meet all eligibility criteria. The investigator will maintain a screening log to record details of all participants screened and to confirm eligibility or record reasons for screening failure, as applicable. Sites will follow the HIV testing algorithm for Screening detailed in [Appendix 9](#) and included in the SRM. If a reactive/positive result is obtained for any HIV test, the person is not eligible for the study. Additional testing to confirm suspected HIV infection during Screening will be performed in accordance. Participants with reactive screening tests for HIV will receive counselling and be referred for further testing and appropriate management.
- Procedures conducted as part of the participant's routine clinical management (e.g., blood count) and obtained before signing of Informed consent form (ICF) may be utilized for screening or baseline purposes provided the procedure met the protocol-specified criteria and was performed within the time frame defined in the SoA ([Table 1](#)).
 - The maximum amount of blood collected from each participant over the duration of the study, including any extra assessments that may be required, will not exceed 1500 mL.
 - Repeat or unscheduled samples may be taken for safety reasons or for technical issues with the samples.

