12.8. Appendix 8: Toxicity Management

ANEMIA

Grade 1 (mild) hemoglobin decrease:

Any hemoglobin decrease meeting the definition of Grade 1 must be repeated with the following additional tests:

1. peripheral blood smear
2. indirect bilirubin (abnormal if increased >50% from baseline)
3. haptoglobin (abnormal if ≤ 25 mg/dL)
4. reticulocyte count (abnormal if $\geq 4\%$)

If the additional tests are within the normal range, participants may continue study medication. If one or more of the additional tests is abnormal or suggestive of hemolytic anemia as specified above, participants will permanently discontinue study medication and be withdrawn from the trial. Participants should be followed up until resolution of anemia.

Grade 2 (moderate) hemoglobin decrease:

Any hemoglobin decrease meeting the definition of Grade 2 must be repeated with the following additional tests:

1. peripheral blood smear
2. indirect bilirubin (abnormal if increased > 50% from baseline)
3. haptoglobin (abnormal if ≤ 25 mg/dL)
4. reticulocyte count (abnormal if $\geq 4\%$)

If the additional tests are within the normal range, participants may continue study medication. If one or more of the additional tests is abnormal or suggestive of hemolytic anemia as specified above, participants will permanently discontinue study medication and be withdrawn from the trial. Consultation with a Hematologist should be considered. Participants should be followed up until resolution of anemia.

Grade 3 (severe) or Grade 4 (potentially life threatening) hemoglobin decrease:

Any hemoglobin decrease meeting the definition of Grade 3 or 4 must be repeated with the following additional tests:

1. peripheral blood smear
2. indirect bilirubin
3. haptoglobin
4. reticulocyte count

Participants will permanently discontinue study medication and be withdrawn from the trial. Consultation with a Hematologist should be considered. Participants should be followed up until resolution of anemia.

TOTAL BILIRUBIN ELEVATION

Grade 1 (mild) bilirubin elevation (1.1 - 1.5 times ULN) or Grade 2 (moderate - 1.6-2.5 times ULN):

Any bilirubin value above the upper limit of normal must be repeated and fractionated (direct and indirect bilirubin). Participants may continue study medication. Participants should be followed up until resolution (return to baseline) of elevation.

Grade 3 (severe – 2.6-5.0 times ULN) or 4 (life-threatening - > 5.0 times ULN) bilirubin elevation:

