Any bilirubin value above the upper limit of normal must be repeated and fractionated (direct and indirect bilirubin). Participants will permanently discontinue study medication and be withdrawn from the trial. Participants should be followed up until resolution (return to baseline) of bilirubin elevation.

AST AND ALT ELEVATION

See Section [12.6](#).

RASH

Grade 1 rash (Localized macular rash):

Participants with Grade 1 rash should be evaluated by the Investigator immediately. A dermatologist may be consulted and a biopsy may be obtained if recommended by the dermatologist. The study drug should be permanently discontinued if the following signs or symptoms are noted at any time:

1. Temperature >38.5°C
2. Lymphadenopathy
3. Pharyngitis
4. Any indication of internal organ involvement (hepatitis, nephritis)

In the absence of the above signs or symptoms, participants with Grade 1 rash may continue the study drug at the discretion of the Investigator. The participant should be advised to contact the Investigator immediately if there is any worsening of the rash, if any systemic signs or symptoms worsen, or if mucosal ulceration develops. If the rash is considered to be most likely due to concomitant illness or non-study medication, standard management, including discontinuation of the likely causative agent, should be undertaken. If no other causative factor is found after clinical evaluation, the participant may be treated symptomatically until the rash resolves. Antihistamines, topical corticosteroids or antipruritic agents may be prescribed. The participant should remain on the study to be followed for safety and PK as outlined in Section [2](#).

Grade 2 rash (Diffuse macular, maculopapular, or morbilliform rash OR Target lesions):

Participants with Grade 2 rash should be evaluated by the Investigator immediately. Digital photographs should be obtained. A dermatologist may be consulted and a biopsy may be obtained if recommended by the dermatologist. The study drug should be permanently discontinued if the following signs or symptoms are noted at any time:

- Temperature > 38.5°C
- Lymphadenopathy
- Pharyngitis
- Any indication of internal organ involvement (hepatitis, nephritis)

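### Exclusion criterion 15 sets no ceiling on isolated indirect bilirubin, so a man can be eligible while already in Appendix 8's withdrawal band (2.6xULN or more); a rare and minor conflict that one phrase would close

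*Protocol*

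**What the plan says.** **Entry.** Criterion 15 in protocol Section 6.2 excludes men with ALT, ALP or bilirubin of 1.5xULN or more. Its exception reads "isolated bilirubin >1.5xULN is acceptable if bilirubin is fractionated and direct bilirubin <35" per cent, and no maximum follows. The exception looks deliberate, because criterion 1 in the same section excludes liver disease "with the exception of Gilbert's syndrome or asymptomatic gallstones".

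**Stopping.** Appendix 8 (Section 12.8) manages total bilirubin by multiples of ULN. For its Grade 1 and 2 bands, 1.1 to 2.5xULN, it says "Any bilirubin value above the upper limit of normal must be repeated and fractionated (direct and indirect bilirubin). Participants may continue study medication". The next instruction covers Grade 3, printed as 2.6 to 5.0xULN, "or 4 (life-threatening - > 5.0 times ULN) bilirubin elevation". There the action is: "Participants will permanently discontinue study medication and be withdrawn from the trial". Fractionation is ordered again, but its result does not alter the action. Baseline appears only as the end of follow-up: "Participants should be followed up until resolution (return to baseline) of bilirubin elevation".

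**Grading.** SAP 7.1.3 grades all laboratory tests by protocol Appendix 7 and tabulates Grade 2 or higher events by study phase. For adults, Appendix 7 ends Grade 2 total bilirubin just below 2.6xULN. It attaches signs and symptoms of hepatotoxicity to Grade 3, and life-threatening consequences to Grade 4.

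**The concern.** The two rules are written on the same scale and their ranges overlap. A healthy volunteer with a stable, mainly unconjugated bilirubin at or above 2.6xULN meets criterion 15, yet on the printed bands of Appendix 8 he should stop at once although nothing about him has changed. If he is dosed, the next scheduled chemistry after Day 1 is Day 28. Section 8.1 takes anyone who stops in the oral phase out of the study, and Section 6.4 bars re-screening once oral cabotegravir has been given. He would have taken study drug to no purpose, and the site would hold an eligibility rule and a stopping rule that disagree.

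Bilirubin is also a test that matters here. Section 5.5 expects that carriers of reduced-function UGT1A1 variants may be predisposed to a rise in total bilirubin. The primary safety analysis counts Grade 2 or higher laboratory events, so a bilirubin value that falls outside every printed grade weakens the count where a signal is most plausible.

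**Working it through.** The plan gives no figure to reproduce. The check compares threshold ranges.

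**1. Overlap of entry and stop**
- Admitted by the exception: total bilirubin >1.5xULN, direct fraction <35%, no upper bound (Section 6.2).
- Withdrawal band: total bilirubin 2.6xULN or more, any fraction, any baseline (Appendix 8).
- Intersection: every isolated value of 2.6xULN or more with direct fraction <35%.

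Illustration with assumed values: total bilirubin 3.0xULN, direct fraction 20%, normal ALT and ALP. He passes criterion 15 and lies in Appendix 8's 2.6 to 5.0xULN band before his first dose.

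**2. Rise needed to reach the stop**

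Rise = 2.6 / entry value - 1.

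| Entry value (xULN) | Calculation | Rise to stop |
|---|---|---|
| 2.6 or more | already in band | 0% |
| 2.5 | 2.6/2.5 - 1 | 4.0% |
| 2.0 | 2.6/2.0 - 1 | 30.0% |
| 1.6 | 2.6/1.6 - 1 | 62.5% |

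The contradiction proper is confined to the first row.

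**3. Comparison with other tests**
- Haemoglobin: entry requires at least 11 g/dL; Appendix 8 actions begin at Grade 1, whose upper end in Appendix 7 is 10.9 g/dL. No overlap.
- ALT: entry requires <1.5xULN; the Appendix 6 stop is 3xULN or more. No overlap.

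The bilirubin overlap therefore looks like an oversight.

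**4. Size for one man**
- Share of oral-phase entrants: 1/48 = 2.1%.
- Oral exposure by the Day 28 chemistry: up to 28 x 30 mg = 840 mg, unless the Day 1 result or the investigator stops him sooner.

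**5. Appendix 7 grade of an asymptomatic value**
- 1.1 to <1.6xULN: Grade 1.
- 1.6 to <2.6xULN: Grade 2.
- 2.6xULN or more: no printed grade, because Grades 3 and 4 both carry a clinical condition.

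If a man's only elevated values in a phase are 2.6xULN or more, his bilirubin is missed in Table 2.16 (Grade 2 or higher tests), Table 2.22 (grade shifts) and Listing 28. If he also has a Grade 2 value in that phase, Table 2.16 already counts him, and so does the maximum-grade shift; only a by-visit shift cell changes.

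**The case against.** The strongest objection is that the stop may not apply. Appendix 8 labels its band Grade 3, and Appendix 7 makes 2.6 to <5.0xULN Grade 3 only with signs of hepatotoxicity. A site grading by Appendix 7 might leave an asymptomatic man on treatment. This stands as a reason for caution, but it does not reconcile the texts. Appendix 8 prints its own numeric range without the clinical condition, and it is the section that prescribes the action. Nor can elevation be assumed to mean a rise from baseline: the anaemia section of the same appendix writes out a baseline-relative rule for indirect bilirubin (an increase of more than 50%), whereas the bilirubin section does not.

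Several provisions may intercept him:
- The schedule of activities requires eligibility to be reviewed against Day 1 assessments.
- Inclusion 5 and exclusion 5 leave room for physician judgement.
- Section 8.2.1 asks for one confirmatory repeat and adds: "Before discontinuing a participant from investigational product(s), the Investigator must contact the Medical Monitor".
- Section 5.2 allows oral-phase dropouts to be replaced, so the target of about 40 men in the injection phase need not suffer.

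All of these reduce the harm. None exempts an unchanged baseline value. A repeat does not help if the value is stable, Section 8.1.2 forbids a temporary hold, and Section 9 states: "Protocol waivers or exemptions are not allowed". The AE definition in Appendix 4 leaves out pre-existing conditions that do not worsen, but it governs reporting, not stopping. Appendix 6 is triggered by ALT. The liver stopping algorithm in Section 8.1.1 is a figure not shown in the text reviewed, so it could bear on the question.

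On frequency, the documents report nobody at 2.6xULN. Section 5.5 mentions five participants with on-treatment bilirubin of at least 1.5xULN (dataset size not given) and mild Grade 1 to 2 rises in an earlier study.

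**Conclusion.** The conflict is real but minor. On the printed text, a man can satisfy criterion 15 while already in Appendix 8's withdrawal band, and no visible provision exempts him. The number affected cannot be derived from the documents and is probably very small. The conclusion rests on reading Appendix 8's bands as numeric and on the unseen Section 8.1.1 algorithm not resolving the matter.

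A reader might infer that such a man is certain to be dosed for 28 days and then withdrawn. The documents do not support that: he may be stopped at screening, at Day 1 review or after Medical Monitor contact, and Appendix 7 gives a site a ground for not applying the stop. A reader might also infer that high bilirubin values vanish from the safety report. They do not. The hepatobiliary abnormality table (SAP 8.5.6), the clinical-concern threshold of 1.5xULN (SAP 10.8.1) and the chemistry listing all keep him visible. Only the grade-based displays are affected, and only to the extent set out in step 5.

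**What to change.** **Protocol, criterion 15.** Cap the exception: *isolated bilirubin >1.5 to <2.6xULN is acceptable if fractionated and direct bilirubin <35%*. Leave the Appendix 8 stop as it is. This removes only the 0%-change case; a man admitted at 2.5xULN still reaches the stop with a 4% rise. Exempting isolated indirect elevation in Appendix 8 would be an alternative, but it loosens a safety rule, so the cap is preferable.

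**SAP 7.1.3.** Add one sentence: total bilirubin is graded by the numeric bands of protocol Appendix 8 or, alternatively, a value of 2.6xULN or more without symptoms counts as at least Grade 2, in Tables 2.16 and 2.22 and Listing 28.

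**Cost.** One phrase by amendment and one SAP sentence. Criterion 15 already requires fractionation, so no new test is needed. The downside is perhaps an occasional extra screen failure.
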